After data collection has concluded for the main RCT, we will conduct Optional Research to enhance our pilot and feasibility exploration and reporting. Participants will include health care providers and research assistant staff who were involved in recruiting youth participants for the RCT.

Health care providers who were involved in study recruitment will be invited to complete an electronic survey. The purpose is to help us learn about their experience recruiting youth during the pandemic and about their perspective on integrating the eHealth intervention into practice. Each health care provider participant will have the opportunity to be entered into a draw to win a \$250 meal allowance for their next staff meeting. Rather than a guaranteed gift card incentive of low monetary value (e.g., \$10 for each of 25 respondents), we have selected a lottery model which will give survey respondents a chance at a more appealing incentive. We feel this incentive is appropriate and reasonable in scope in order to encourage participation without undue inducement.

Research Assistant (RA) staff who were involved in study recruitment will be invited to participate in a focus group interview by Zoom and to complete a short demographic survey. The purpose of the focus group is to help us learn more about the processes, resources, and management of the study. As a token of appreciation for their time to participate, all research assistant participants will be given a \$25 gift card. We expect to include 10-12 participants.

SAMPLE

Our primary sample will be comprised of 264 youth with BBD, between 15 and 17 years of age, who are recruited through a participating clinic in one of the four study regions (Alberta, Ontario, Quebec, and Maritimes) and who are at least 6 months pre-transfer to the adult health care system. A parent/caregiver of the youth will also be recruited to the study. The study aims to have an equal

NOTE: CTO#1666 Amendment approved by HiREB on January 9, 2023. Target sample was 264 participants; however, we randomized 52 participants, and did not complete the full-scale RCT. Linking health card numbers with provincial administrative data is labour intensive and costly, and the small number would not provide meaningful results. As approved by ethics, we dropped the health economic outcome analysis (Health card number linking, Health Utilities Index (HUI), Resource Use Questionnaire (RUQ)) and destroy stored health card number data.

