number of participants in each of two groups: intervention group (132) and control group (usual care) (132). Since participants will be recruited from only four regions, we will model the effect of region as a fixed effect rather than a random effect.¹⁸ This will allow region-specific intervention effects to be modelled (i.e. region by intervention interaction effects). If no region by intervention interactions are found, the interaction terms will be dropped from the model and we will estimate an overall intervention effect. Since the region by intervention interaction is unknown, we take a conservative approach with a sample size calculation that will enable detection of an intervention effect within each site. This will allow for a properly powered analysis of the site by treatment interaction. The primary outcome measure (Transition Readiness Assessment Questionnaire, TRAQ)⁹ has been validated on a sample of youth with congenital heart disease and in the absence of literature specific to BBD, we will base our sample size calculations on these findings. We anticipate a mean TRAQ self-management baseline score of 3.01 (SD 1.02) (out of a possible 5.0) as reported for youth (with congenital heart disease) without a transition intervention and an anticipated mean score of 4.0 at 6 months post-intervention resulting in a change score of 1 (i.e., 1 SD), with $\alpha=0.05$ and 90% power.¹⁹ Therefore, in each region, we will require 23 youth in each of the 2 arms (total of 46) x 4 regions = 184. Estimating 30% attrition, we will enroll 264 participants.

Inclusion Criteria

- Youth with chronological age between 15 and 17 years of age (i.e. before 18th birthday), in one of the four study regions, followed in pediatric care and for whom a discharge from pediatric care is planned but not for at least 6 months.
- A diagnosis of one of the following neurological BBD: autism spectrum disorder, cerebral palsy, epilepsy, spina bifida, or fetal alcohol spectrum disorder.
- Cognitive ability to provide informed consent and the ability to read and understand English or French
- Access to internet and a smartphone, iPad/tablet or desktop computer.
- TRANSITION-Q²⁰ score >40 (as a screen to define a minimum threshold for transition readiness based on our earlier work).

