In terms of exposure time, there is planned flexibility to allow participants to proceed through the MyREADY Transition™ BBD App intervention at their own pace. The App has 19 individual sections organized within 5 chapters that are provided within a set order. A timer has been built into the App to ensure that participants will have at least one day between sections. This will allow for time to process and reflect on the take-away message in each section and/or engage in one of the suggested between-session practice activities. The timer will help to moderate pace and align with how young people learn and digest information. We estimate that there are approximately 5-7 hours of content within the 5 chapters of the App, depending on individual pace. For the RCT, the recommended exposure to the intervention is somewhere between 1 section per day (19 days) and 1 section per week (19 weeks). As an example, if a participant completed one of the five chapters per week, they would complete the App in 5 weeks. Games and fun activities are incorporated to encourage youth to visit the App between sections. The tools and resources within the App remain available for users to access throughout the intervention exposure time. The researchers aim to supply the MyREADY Transition™ BBD App to participants in both the intervention and control group for a limited time after their participation in the study. However, if the App intervention turns out not to be effective, or if significant issues are found, study participants may not be able to access the App. We will continually review and update our securities and controls as technology changes to ensure ongoing personal information security. In case of substantial impactful changes of the main technical elements (components and services) including but not limited to iOS, Android, Web or the CMS; the team may discontinue the support of the application and therefore withdraw the App. Any changes we may make to our privacy statement in the future will be posted on the platform page and, where appropriate, notifications will be sent to users by e-mail.

We know that the experiences of youth, parents/caregivers and service providers are interconnected and interdependent.²⁵ We expect that in both groups, the parent(s)/caregiver(s) and health care

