Primary: To determine whether the MyREADY Transition™ BBD App intervention will result in improved transition readiness	Primary: 
 Change in TRAQ self-management score from Baseline to 6 months. 	Intervention > Control	T-Test; p<0.05
	Secondary: 
 Change in TRAQ self-advocacy score from Baseline to 6 months. 	Intervention > Control	T-Test; p<0.05
	Secondary 
 Health care transition experience 	Individual semi-structured interviews	Qualitative Methods
Secondary: What is the effect of the MyREADY Transition™ BBD App intervention for	Primary: Population Health 
 Serious illness (hospitalizations, ICU admission questions from Resource Use Questionnaire 	Intervention > Control	T-Test for continuous outcomes Chi-square test

NOTE: CTO#1666 Amendment approved by HiREB on January 9, 2023. Target sample was 264 participants; however, we randomized 52 participants, and did not complete the full-scale RCT. Linking health card numbers with provincial administrative data is labour intensive and costly, and the small number would not provide meaningful results. As approved by ethics, we dropped the health economic outcome analysis (Health card number linking, Health Utilities Index (HUI), Resource Use Questionnaire (RUQ)) and destroy stored health card number data.

improving health and use of health systems?	
 • PedsQL™ Pediatric Quality of Life • Patient Activation Measure (PAM) (health-related self-efficacy) • TRANSITION-Q 		for hospitalization
	Secondary: 
 • Utilization MyREADY Transition™ BBD App 	User metrics built into MyREADY Transition™ BBD App intervention to assess the extent to which various components of the intervention are accessed	Descriptive
	Secondary: Cost utility/cost-effectiveness 
 • Health Utilities Index® (Hui2/3) • Resource Use Questionnaire 	Evaluate changes in patients' health in relation to changes in cost to assess if the intervention represents an efficient allocation of health care resources	Descriptive; Cost-effectiveness analysis with support from Child-Bright health economics network team

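### With 52 of 264 randomised, the claims of 90% power within each region and a powered region-by-intervention interaction no longer hold, yet the plan keeps them and the interaction-first rule

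*Combined protocol and SAP*

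**What the plan says.** The SAMPLE section takes region as a fixed effect with a region-by-intervention interaction. If no interaction is found, those terms are removed and one overall effect is estimated. Because the size of the interaction was unknown, the section adopts a "sample size calculation that will enable detection of an intervention effect within each site" and adds: "This will allow for a properly powered analysis of the site by treatment interaction". The inputs are a baseline SD of 1.02, a rise from 3.01 to 4.0 treated as one SD, and the calculation is made "with $\alpha=0.05$ and 90% power". This gives 23 per arm and 46 per region, 184 over four regions, and 264 after 30% attrition.

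The note repeated throughout the document, including within SAMPLE, says: "Target sample was 264 participants; however, we randomized 52 participants, and did not complete the full-scale RCT". It drops the health-economic analysis, giving two reasons: linkage to administrative data is laborious and expensive, and the small number would not be informative.

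Table 1 (STATISTICAL ANALYSIS) sets the criterion for the primary outcome, change in TRAQ self-management score, as "Intervention > Control", tested by a t-test at the 0.05 level. That row is not divided by region.

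**The concern.** The amended document describes two different trials. One has 184 evaluable youth and can look for an effect region by region. The other has 52 randomised youth. The note adjusts the health-economic plan to the smaller trial, but nothing adjusts the power statement or the modelling sequence for effectiveness.

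The modelling sequence is where this affects the analysis. The plan looks for an interaction first and moves to a single overall effect if none is found. That step is defensible only if the test could find an interaction that matters. With about 36 to 52 youth in eight region-by-arm cells it mostly could not. Failing to find one would then say little about whether regions differ, while the text tells the reader that the test was adequately powered. If a chance interaction were found, the primary result would become four regional estimates, each resting on a handful of youth.

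**Working it through.** **Inputs from the documents.** Two arms, 1:1, stratified by region (Randomization); four regions, alpha 0.05, 90% power, SD 1.02, effect 1 SD, 30% attrition (SAMPLE); 52 randomised (note). Sidedness is not stated. A one-sided test would need only 18-19 per arm, so the plan's 23 implies a two-sided test.

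**Inputs not in the documents, taken as assumptions.** The regional split of the 52 and the number with 6-month data are not given. I assume an even split (13 per region) and show attrition from 30% to zero. The 0.5 SD effect and the pattern of regional effects used for the interaction are illustrations.

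**1. The plan's own figure.** For a two-sided t-test, the noncentrality is d × √(n1·n2/(n1+n2)) with n1+n2−2 degrees of freedom. At 23 per arm, power is 91.2% for d = 1 and 90.2% for d = 1/1.02. For attrition, 46/0.7 rounds up to 66 per region, and 66 × 4 = 264. The planned size reproduces.

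**2. Can the claim hold for any split of 52?** It needs 46 evaluable in every region, 184 in all. With no attrition at all, a region holding 46 leaves 52 − 46 = 6 for the other three. At most one region could reach the required size.

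**3. Power within a region, even split, d = 1.**

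- 30% attrition: 13 × 0.7 = 9.1 per region, so 4-5 per arm; 52 × 0.7 = 36.4, so about 36 analysed.
- No attrition: 6-7 per arm, 52 analysed.

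| Per arm | Separate t-test | Model's pooled residual variance |
|---|---|---|
| 4 and 4 | 22.3% | 27.7% (28 df) |
| 5 and 4 | 25.2% | 30.2% (28 df) |
| 5 and 5 | 28.6% | 33.3% (28 df) |
| 6 and 6 | 34.7% | 39.5% (44 df) |
| 7 and 6 | 37.5% | 42.0% (44 df) |

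The residual degrees of freedom are the number analysed minus eight cells: 36 − 8 = 28 and 52 − 8 = 44. Uneven splits widen the spread: with separate t-tests, a region with 4 evaluable youth has 9.5% power and one with 20 has 56%.

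**4. Interaction test (3 df).** Illustration: effect 1 SD in two regions, zero in two, equal regions with m per arm. Each regional effect lies 0.5 SD from the mean of 0.5 SD, so the noncentrality is 4 × (m/2) × 0.5² = m/2.

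| Analysed | m | Noncentrality | Power |
|---|---|---|---|
| 36 | 4.5 | 2.25 | 19% |
| 52 | 6.5 | 3.25 | 27% |
| 184 (planned) | 23 | 11.5 | 81% |

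**5. Pooled t-test (Table 1).**

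| Per arm | d = 1 | d = 0.5 (assumed) |
|---|---|---|
| 18 (30% attrition) | 83.0% | 31% |
| 26 (no attrition) | 94.2% | 42% |

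Adding region as a main effect costs almost nothing: 82.8% instead of 83.0% at 18 per arm.

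**6. Precision of the pooled estimate.** The half-width of the 95% CI is t × 1.02 × √(2/18) = 2.03 × 1.02 × 0.333 = 0.69 TRAQ points with 36 analysed.

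**The case against.** The shortfall is disclosed openly and repeatedly, and the SAMPLE text can be read as the forward-looking rationale for 264. The plan already mentions pilot and feasibility reporting and cites the CONSORT extension for pilot trials. All of this is true. But the pilot and feasibility wording in the Internal Pilot Phase section introduces optional research with providers and research staff. The CONSORT sentence covers the pilot phase and the main RCT without changing the status of the primary test. No sentence says which analysis applies to 52 youth.

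The decision to keep the effectiveness analysis is also less inconsistent than it may look. Cost was one of the two reasons for dropping the health-economic work, and it does not apply to TRAQ questionnaires.

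Three stronger readings are tempting, and the documents do not support them:

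- **That the p<0.05 criterion has only 22-38% power.** A reader might infer this by setting the regional figures beside Table 1. The Table 1 test is pooled, and at the plan's own 1 SD it keeps 83-94%.
- **That a false negative is likely.** At 1 SD the pooled risk is about 6-17%. It becomes likely only at smaller effects such as 0.5 SD, a value that the documents do not contain.
- **That p≥0.05 will be taken as proof of failure and end access to the App.** The section Intervention and Control Conditions says that "if the App intervention turns out not to be effective, or if significant issues are found, study participants may not be able to access" it, but names no p-value rule. Nowhere does the plan equate non-significance with an ineffective App.

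**Conclusion.** The point stands for the within-region and interaction claims. That they no longer hold at 52 needs no assumption about the split, attrition or effect size. How far power falls does rest on assumptions: about 22-38% per region with separate t-tests, or 28-42% with the pooled residual variance, given an even split, a 1 SD effect and 30% to zero attrition. The 19-27% for the interaction also rests on the illustrative pattern of regional effects. With power that low, finding no interaction would be uninformative and should not decide the form of the primary analysis.

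The pooled comparison remains reasonably powered if the true effect is as large as planned, and not if it is about half that. The defect is therefore an outdated power claim and an unsuitable gatekeeping step; the pooled primary test itself remains usable.

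**What to change.** Keep the derivation of 264 as history and add a dated statement beside it, with these elements:

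1. **Delivered size and power.** 52 randomised; actual numbers by region and with 6-month data; pooled power 83-94% at 1 SD for 18 to 26 per arm. Label any other effect size, such as 0.5 SD, as an assumption.
2. **Withdrawn claims.** State that within-region detection and a powered interaction no longer apply.
3. **Primary analysis.** One pooled intervention effect with region as a main effect and no interaction test as gatekeeper. Show regional results descriptively.
4. **Reporting.** Give the estimate with its 95% CI (half-width about 0.7 TRAQ points with 36 analysed, SD 1.02) as pilot-scale evidence under the CONSORT pilot extension already cited. State that an interval including zero does not show that the App is ineffective.

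The cost is a change of wording, a less favourable stated power and a non-confirmatory claim. No further enrolment is needed.

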We will request consent to obtain youth participant's Health Card Number to answer questions about use of health services like physician office visits, visits to emergency rooms and hospitalizations during

NOTE: CTO#1666 Amendment approved by HiREB on January 9, 2023. Target sample was 264 participants; however, we randomized 52 participants, and did not complete the full-scale RCT. Linking health card numbers with provincial administrative data is labour intensive and costly, and the small number would not provide meaningful results. As approved by ethics, we dropped the health economic outcome analysis (Health card number linking, Health Utilities Index (HUI), Resource Use Questionnaire (RUQ)) and destroy stored health card number data.

the study period (between the time a participant joins the study up until March 31, 2021). Participants have the option of participating in the study without sharing the youth's Health Card Number. The Health Card Number will allow us to link the information provided in the study with provincial data regarding the participant's use of health services. We will work with appropriate organizations in each province (Alberta, Ontario, Quebec, New Brunswick, and Nova Scotia) to gain approval to access provincial Health Services Administrative Data repositories. Health care services data recorded in the provincial administrative databases will be linked deterministically to the study data using the Health Card Number, partial date of birth and sex.

STATISTICAL ANALYSIS:

We will use regression analysis to adjust for baseline function as a sensitivity analysis to address any residual imbalance from the randomization.

The analysis and reporting of the internal pilot phase and main RCT results will follow CONSORT guidelines²³⁻²⁴. Patient demographics and baseline outcome variables (both primary and secondary) will be summarized using descriptive summary measures. All analyses will be performed using SAS 9.4 (Cary, NC). Analysis will be intention to treat. The table below provides a summary of study objectives, corresponding outcomes, hypotheses and methods of analyses. For subgroup analysis we will use interaction test (interaction of subgroup variable with the treatment or intervention variable).

Table 1: Study Objectives, Corresponding Outcomes, Hypotheses and Methods of Analyses

Objective	Outcome	Criterion for Success	Method of Analysis

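### Sizing each region for its own 1 SD effect does not give a properly powered region-by-treatment interaction, and the SAMPLE section's region model is not the t-test in Table 1

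*Combined protocol and SAP*

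**What the plan says.** All quotations are from the combined protocol and SAP.

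- **SAMPLE, model.** Because there are only four regions, "we will model the effect of region as a fixed effect rather than a random effect". The stated purpose: "This will allow region-specific intervention effects to be modelled (i.e. region by intervention interaction effects").
- **SAMPLE, decision rule.** "If no region by intervention interactions are found, the interaction terms will be dropped from the model and we will estimate an overall intervention effect". No level is given for the test that decides this, and nothing is said about the case where an interaction is found.
- **SAMPLE, sizing.** The reason given for the approach is "Since the region by intervention interaction is unknown". The approach itself is described in these terms: "we take a conservative approach with a sample size calculation that will enable detection of an intervention effect within each site". The calculation uses a 1-point (1 SD) difference, a baseline SD of 1.02, alpha 0.05 and 90% power. It gives 23 per arm per region, 184 in total, and 264 with 30% attrition. The plan draws this conclusion from the within-region sizing: "This will allow for a properly powered analysis of the site by treatment interaction".
- **STATISTICAL ANALYSIS.** "We will use regression analysis to adjust for baseline function as a sensitivity analysis". It also plans an interaction test for subgroups, without naming any. On Table 1: "The table below provides a summary of study objectives, corresponding outcomes, hypotheses and methods of analyses".
- **Table 1.** For change in TRAQ self-management, the primary outcome, the method is a t-test at the 5% level with no region term and no condition.
- **SYNOPSIS and Randomization.** The synopsis says the analysis is stratified by region, and randomisation is stratified by region.
- **2023 note.** 52 of 264 were randomised. The note drops the health-economic analyses only.

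**The concern.** There are two linked problems.

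First, power for a treatment effect inside one region is not power for a difference in that effect between regions. The plan sizes for the former, gives no magnitude for the latter, and then claims both. This matters because the drop rule acts on a between-region test. If that test has little power, finding no interaction will often be misread as agreement between regions.

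Second, the primary analysis is not uniquely defined. The SAMPLE section describes a region model whose result depends on the interaction test, while Table 1 gives an unconditional t-test. If an interaction were found, the documents would not settle whether the regional effects or the t-test is the primary result, or how four regional tests would be handled. The choice could then be made after the data are seen.

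**Working it through.** **Inputs from the plan.** Difference 1 point; SD 1.02 (a baseline SD; no change-score SD is given); alpha 0.05; 23 per arm in each of 4 regions; 30% attrition. Two-sided testing is inferred: a one-sided calculation gives 18 to 19 per arm, not 23.

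**Step 1. Reproduce the plan's figure.** A two-sample t-test with 23 per arm and difference 1 has power 0.902 at SD 1.02 and 0.912 at SD 1.00. Then 23 × 2 × 4 = 184, and 184/0.7 = 262.9. Rounding each cell up to 33 gives 33 × 8 = 264. The arithmetic is sound.

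**Step 2. Contrasts between regions (176 df).** The variance of one region's effect is 2 × 1.02²/23 = 0.0905, so its SE is 0.301.

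| Contrast | SE | Power, 1 point | Power, 0.5 point | Detectable at 90% |
|---|---|---|---|---|
| One region v one | √(2 × 0.0905) = 0.425 | 65% | 22% | 1.39 |
| One v three | √(0.0905 × 4/3) = 0.347 | 82% | 30% | 1.13 |
| Two v two | √(0.0905 × 1) = 0.301 | 91% | 38% | 0.98 |

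**Step 3. Global interaction test.** F with 3 and 8n − 8 df, alpha 0.05 assumed, noncentrality = S/(2·SD²/n), where S is the sum of squared deviations of the four regional effects from their mean. The patterns are assumptions. SD 0.79 is 1.02 × √(2 × (1 − 0.7)), for an assumed baseline-to-follow-up correlation of 0.7; SD 1.2 corresponds to about 0.31. The last column spreads the 52 randomised evenly (52/8 = 6.5 per arm per region) with no attrition.

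| Regional effects (points) | S | Noncentrality, n = 23, SD 1.02 | Power, SD 1.02 | SD 0.79 | SD 1.2 | 52 randomised, SD 1.02 |
|---|---|---|---|---|---|---|
| 1, 1, 0, 0 | 1.00 | 11.05 | 80% | 96% | 64% | 26% |
| 1, 1, 1, 0 | 0.75 | 8.29 | 66% | 88% | 51% | 20% |
| 1, 1, 0.5, 0.5 | 0.25 | 2.76 | 25% | 40% | 19% | 10% |
| 1, 1, 1, 0.5 | 0.1875 | 2.07 | 19% | 31% | 15% | 8% |
| 1, 1, 1, −0.5 | 1.6875 | 18.65 | 96% | – | – | – |

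Simulation of 20,000 trials at SD 1.02 gave 79.6%, 65.9%, 24.9%, 19.7% and 96.0%, and 5.0% when all effects were equal.

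**Step 4. Compare the two descriptions of the primary analysis.**

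- Region: a fixed effect with interaction terms in SAMPLE; absent from Table 1. The synopsis and the stratified randomisation agree with SAMPLE.
- Overall effect: in SAMPLE, promised for the case where no interaction is found; in Table 1, unconditional.
- Interaction found: neither place says which result is then primary.
- Regression: the STATISTICAL ANALYSIS text mentions it only as a sensitivity analysis for baseline function. Its subgroup interaction test names no region and no primary model.

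**Step 5. What the open branch could cost.** Assume, since the plan does not say so, that any single region with p < 0.05 counts as success once an interaction is found, and that the pooled region-adjusted test is used otherwise. With no true effect and 23 per arm per region (200,000 simulated trials), the false-positive rate is about 9.4% two-sided, and about 5% in favour of the App, if the interaction is judged at p < 0.05. Judged at p < 0.20, the rates are about 16% and 8.5%. One pooled test gives 5% and 2.5%.

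**The case against.** **The plan defines its own term.** It glosses interaction effects as region-specific effects, and those are powered. This stands as far as it goes. It does not rescue the claim, because the drop rule needs a test of differences between regions, and that test was not sized.

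**The low power figures depend on chosen patterns.** True. Power runs from 15% to 96% over the four main patterns and the SD range, and some cases exceed 90%: one region reversed, a two-v-two contrast, or a smaller SD. So the figures do not show failure against a stated target. They show that no target was stated and that the power asserted does not follow from the sizing.

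**Table 1 is only a summary.** Its t-test could mean the test of the treatment coefficient in the region model, and the plan never calls a regional result primary. That is a possible reading, but no text adopts it, and it still leaves open what follows a found interaction.

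**The error rates rest on an assumed success rule.** Correct. Under Table 1's unconditional test the error is 5%. The inflated figures show what the ambiguity permits, not what the plan prescribes.

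**The trial stopped at 52.** The sizing sentence is therefore largely historical. The decision rule and Table 1 still govern the TRAQ analysis, and at this size an absence of detected interaction says almost nothing.

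**Conclusion.** The concern holds and should be fixed. The sample size is right for within-region effects, and the pooled comparison was well powered as designed. The interaction claim is unsupported: at the plan's SD, power is 65% for a 1-point difference between two regions, and between 19% and 80% for the four main patterns. About 90% is reached only under large heterogeneity or favourable assumptions. All of this rests on assumed regional patterns and on using the baseline SD for change scores.

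The ambiguity over the primary analysis needs no such assumptions, since it follows from the text. If no interaction is found, the harm is limited to over-reading that result. If one is found, the primary result is open to choice after the fact. On the assumed any-region reading, the chance of a false claim for the App roughly doubles, from 2.5% to about 5%.

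**What to change.** Make these changes before unblinded outcome data are seen (the Randomization section says the analysis will be blinded). If data have already been seen, date the change and report it as post hoc.

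1. In SAMPLE, delete the sentence claiming a properly powered interaction and state that the sample was sized for within-region effects.
2. Make the treatment effect adjusted for region as a main effect (the randomisation stratum) the primary estimate, whatever the interaction test shows. Align SAMPLE and Table 1 to it; the synopsis can stay.
3. Remove the drop-if-not-found rule. Report regional effects and the interaction as exploratory, with 95% confidence intervals.
4. For the 52 randomised, rely on the confidence interval. Its half-width is t(N − 5) × 1.02 × √(4/N): about 0.57 points at N = 52, or 0.69 if the planned 30% attrition applies (N = 36.4). Optionally, restate planned pooled power as 90% for about 0.48 SD at 184 evaluable.

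The cost is wording in SAMPLE and Table 1, with no extra participants. It is a late change that must be disclosed. The plan gives up any confirmatory regional claim, and the primary estimate becomes an average over regions if they truly differ.
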